12.0 REGULATORY

Any changes made to the protocol will be initiated by the Protocol Chair, and submitted to KUMC IRB (HSC) for approval. After KUMC IRB approval, collaborating sites will submit revised protocol changes to local IRBs for review.

The determination of the necessity to cease enrollment until revisions are approved will be determined by the Protocol Chair.

Appendix 1 – Biomarkers and Testing Procedures

1. Measurement of Serum Hormones

Serum will be stored at -80°C until assay. Pre and post study samples will be run together to avoid batch variation.

Estradiol and SHBG will be assayed directly in serum by commercial kits from Diagnostics Biochem Canada Inc. The estradiol kit # CAN-E-430 (direct EIA); serum only) has a limit of detection of 10 pg/ml; intra-assay precision (CV) of 4.6-9.3%; inter-assay precision (CV) of 6.2-10.1%. SHBG (Direct ELISA) Diagnostics Biochem Canada Inc. kit # CAN-SHBG-4010 has a limit of detection of 0.1 nmol/L; intra-assay CV of 3.0-8.6%; inter-assay CV of 7.2-11.6%.

2. Measurement of Anti-Mullerian Hormone

Anti-Mullerian hormone will be assayed using commercial kits available from Beckman-Coulter (Brea, CA). Serum will be directly assayed using sandwich ELISA kits (#A16507); limit of detection is 1 pM (1 ng/ml = 7.14 pM), intra-assay CV ≤12.3%, inter-assay CV≤14.2%.

3. Measurement of Serum Adipokines, Cytokines,

Serum is collected in clinic, divided into 1-2 ml portions in cryovials and immediately frozen at -80°C prior to transfer to [name] at University of Texas at Austin. Luminex Multiplex Cytokine Assays, adipokine Luminex Multiplex Endocrine Assay kits will be used according to kit directions.

4. Measurement of Serum IGF-I and IGFBP-3

IGF-I and IGFBP-3 will be performed from serum which has been stored frozen in aliquots at -80°C until analysis. Pre and post study samples will be run together. IGF-I and IGFBP-3 will be assayed by ELISA with the standard kits from R&D Systems (Minneapolis, MN). Aliquots of pooled sera will be used to assess inter and intra batch variation. Molar ratio of IGF-I/IGFBP-3 will be calculated as [.130 X IGF-I (mg/ml)]/[.036 X IGFBP-3 ng/ml].

The IGF-I kit (#DG100) is a sandwich ELISA kit with intra-assay CV 3.5-4.3%; inter-assay CV 7.5-8.3%; limit of detection 0.026 ng/ml.

The IGFBP-3 kit (# DGB300) is a sandwich ELISA kit with intra-assay CV 2.3-5.0%; inter-assay CV 5.4-8.0%; limit of detection 0.05 ng/ml.

5. Breast Tissue Assays

Fixed tissue will be stored at room temperature in the original collection tube of Cytolyt® for a minimum of 24 hours prior to transfer to PreservCyt® in the Breast Cancer Prevention Laboratory. Cells may remain in PreservCyt® for up to 1 year before processing to micro-dissection for RNA harvest.

Frozen tissue in the cryovials will be pooled and aliquoted in the Breast Cancer Prevention Laboratory for later assessment of tissue, adipokines and cytokines via luminex, and phosphorylated intermediates of the PI3 kinase and AKT/mTOR using reverse phase proteomics. Cryovials are thawed in a cold tap water bath and immediately placed on ice. A 1000 µl pipettor is used to mix sample in each cryovial and pool all samples for 1 patient in a sterile snap-cap polypropylene tube on ice. An aliquot of a 10X cocktail of PhosSTOP phosphatase inhibitor (Roche Applied Science, Indianapolis, IN) and complete protease inhibitor (Roche) is added to bring the combined inhibitors to 1X. 250 µl samples are aliquoted into 4 or more cryovials and refrozen for retention or shipping to the responsible assay laboratory.

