1.0 OBJECTIVES

The overall objective is to determine whether the natural flaxseed lignan, secoisolariciresinol diglycoside (SDG), in amounts providing plasma lignan levels associated with reduced breast cancer risk, will favorably modulate risk biomarkers for breast cancer development. This will provide biologic evidence of SDG's potential for breast cancer chemoprevention. Based on a positive pilot study in which both Ki-67 and the proportion of women with atypical cytomorphology was reduced with 12 months of SDG 50 mg/day, a randomized, placebo-controlled clinical chemoprevention trial will be conducted wherein pre-menopausal women at increased risk for the development of breast cancer will receive Brevail® (200 mg, equivalent to 50 mg of SDG) or matched, blinded placebo for 12 months. A total of 242 subjects will be accrued, randomized 2:1 to SDG vs placebo, with the goal of achieving 220 subjects completing study and evaluable for biomarker change.

The primary objective is to determine if women randomized to 12 months of SDG exhibit greater change in the proportion of breast epithelial cells expressing the proliferation marker Ki-67/MIB-1 in hyperplastic benign breast tissue than do women randomized to placebo.

Secondary objectives are:

- 1) to determine if 12 months of SDG is associated with favorable modulation of other risk biomarkers including cytologic atypia, and serum levels of bioavailable estradiol and testosterone, IGF-I:IGFBP-3 ratio, c-peptide, adiponectin, and leptin.
- 2) to determine if Ki-67 and modulation of other risk biomarkers is correlated with change in blood or urine lignans.
- 3) to determine impact or potential impact on quality of life as measured by the BPQ breast pain questionnaire (a modified McGill Pain questionnaire), The Breast Cancer Prevention Trial (BCPT) Symptom Checklist a menstrual diary for cyclicity and cycle length for women not on cycle modulating contraceptives; and antimullerian hormone (AMH), a measure of follicular reserve.

An exploratory objective is to interrogate SDG's mechanism of action through measurement of changes in hormones, growth factors, gene expression, adipokines and cytokines and proteomic signatures.

The overriding hypothesis is that biomarkers assessed both in serum and in hyperplastic breast tissue obtained by RPFNA from high risk pre-menopausal women will be favorably modulated by 12 months of SDG without negatively affecting quality of life.

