11.2 Statistical Analysis

All analyses will be intent-to-treat. All subjects randomized will be evaluable for safety and all subjects that have both a pre and post specimen are evaluable for efficacy. Primary analysis of efficacy will be performed on all evaluable subjects and secondary analysis will be done on those subjects who received at least 6 months of study medication and were confirmed as being in the follicular phase for both RPFNA procedures. From our experience we have very little missing data; however, if the missing data rate is above 5%, we will use multiple imputation to impute these values to perform the primary and secondary analyses.

The primary outcome will be change in Ki-67 (percent of cells expressing Ki-67) from baseline to 12 months. The two-sample t-test will be used to compare the change in Ki-67 between the SDG

and placebo groups. Any difference in baseline values of Ki-67 between the two groups would be due to chance, however, if there is a significant difference, then analysis of covariance adjusting for baseline values will be performed. Due to potential skewness in these variables we will assess whether or not the Central Limit Theorem may be assumed. Given the sample size the existence of an extremely high degree of skewness would require the use of the Wilcoxon Signed Rank test.

For the secondary endpoints, similar methods as above will be used to compare the treatment and control groups at two time points for all markers, i.e., serum hormones and clinical laboratory tests. We will also correlate change in the primary biomarker Ki-67 with change in other markers (e.g., bioavailable estradiol, cytokines, RTqPCR results) using Pearson's correlation coefficient. Again, if there exists a high degree of skewness in these variables, Spearman's correlation will be utilized.

Multiple regression analysis will also be used to investigate whether changes in Ki-67 are due to variables other than treatment effect (e.g., age, cytromorphology, Gail risk; as well as the predictive effect of other biomarkers on modulation of Ki-67). Best subsets and stepwise approaches will be employed while controlling for treatment group.

For comparison of moderate or worse toxicities we will consider grade 3 toxicity or premature trial discontinuation as the critical events. The prevalence of events in the SDG vs. the placebo arm will be examined by Fisher's exact test.

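### The IGF-I/IGFBP-3 molar ratio formula in Appendix 1 gives its two analytes in different mass units (mg/ml and ng/ml); both should be in ng/ml

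*Combined protocol and SAP*

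**What the plan says.** Secondary objective 1 in section 1.0 lists the risk biomarkers that SDG is hoped to modulate. Besides cytologic atypia, the list is "serum levels of bioavailable estradiol and testosterone, IGF-I:IGFBP-3 ratio, c-peptide, adiponectin, and leptin".

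The only place that says how the ratio is derived is Appendix 1, item 4 (Measurement of Serum IGF-I and IGFBP-3): "Molar ratio of IGF-I/IGFBP-3 will be calculated as [.130 X IGF-I (mg/ml)]/[.036 X IGFBP-3 ng/ml". No other section restates or amends this rule, and the documents report no ratio value that would show which unit was used.

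The same item describes the two ELISA kits. For IGF-I it gives "inter-assay CV 7.5-8.3%; limit of detection 0.026 ng/ml", and for IGFBP-3 "inter-assay CV 5.4-8.0%; limit of detection 0.05 ng/ml". Both assays are therefore specified in ng/ml.

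For the analysis of secondary endpoints, section 11.2 states that "similar methods as above will be used to compare the treatment and control groups at two time points for all markers". The derived ratio thus goes directly into a planned between-arm comparison.

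**The concern.** A molar ratio divides one molar concentration by another. Fixed multipliers such as .130 and .036 stand for the reciprocals of the two molecular masses, and they give a molar ratio only if the mass concentrations they multiply share a unit. As printed, the numerator takes milligrams per millilitre and the denominator nanograms per millilitre, and nothing in the formula reconciles them. The printed IGF-I unit also disagrees with the kit description that follows it.

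What is at stake is the reported size of one named secondary biomarker: its levels, its change from baseline and the confidence limits on the difference between arms. A derivation rule should give the right number when followed to the letter. If a programmer corrects the unit silently, the result is right but departs from the written plan without a record.

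**Working it through.** The plan states no ratio value, so there is no figure to reproduce. The check is one of dimensions, followed by a check of what a scale error does to the planned tests.

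**Inputs from the documents (Appendix 1, item 4)**
- Factor for IGF-I: 0.130, printed unit mg/ml.
- Factor for IGFBP-3: 0.036, printed unit ng/ml.
- Detection limits: 0.026 ng/ml (IGF-I) and 0.05 ng/ml (IGFBP-3).

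**Step 1: what the factors imply.** If both apply to ng/ml, then 1/0.130 = 7.69 and 1/0.036 = 27.8 ng per pmol, that is, masses of about 7.7 and 27.8 kDa. The same-unit formula is then

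ratio = (0.130/0.036) x (IGF-I/IGFBP-3) = 3.61 x (IGF-I/IGFBP-3).

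**Step 2: the effect of the printed units.** Since 1 mg/ml = 1,000,000 ng/ml, an IGF-I value of x ng/ml is x times 10^-6 mg/ml. Hence

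printed ratio / same-unit ratio = 10^-6,

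whatever the concentrations are. If micrograms were meant, 1 µg/ml = 1,000 ng/ml and the quotient is 10^-3.

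**Step 3: illustration.** The documents give no IGF-I or IGFBP-3 concentrations, so these values are assumed only to show the scale.

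| Assumed IGF-I, ng/ml | Assumed IGFBP-3, ng/ml | Both in ng/ml | IGF-I converted to mg/ml, as printed |
|---|---|---|---|
| 200 | 4000 | (0.130 x 200)/(0.036 x 4000) = 26/144 = 0.181 | (0.130 x 0.0002)/(0.036 x 4000) = 1.81 x 10^-7 |
| 300 | 3000 | (0.130 x 300)/(0.036 x 3000) = 39/108 = 0.361 | (0.130 x 0.0003)/(0.036 x 3000) = 3.61 x 10^-7 |

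**Step 4: the effect on the tests.** Multiply every ratio by the same constant c > 0. The difference in mean change and its standard error are both multiplied by c, so the t statistic does not move. Ranks do not change, so rank tests and Spearman correlations do not move. Pearson correlations are scale-free. In an analysis of covariance the outcome and its baseline are rescaled together, and the treatment test is the same. A simulated change variable (147 and 73 subjects, not trial data) confirmed this for c = 10^-6: the two-sample t-test gave p = 0.100 before and after scaling, and the rank-sum test gave p = 0.172 before and after. Means, differences and confidence limits do shrink by 10^6.

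**Step 5: what else depends on the formula.** Section 11.1 bases sample size and power on change in Ki-67 alone. The stated 83% power (220 evaluable, 2:1, difference 2.5%, SD 6%, two-sided 5%) recomputes to 82.98% and does not involve the ratio.

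**The case against.** The strongest reply is that this is an evident slip with almost no practical consequence. The kit limits in the same item are both in ng/ml, and the plan has no step that converts IGF-I to mg/ml. To obtain the wrong value, someone would have to convert one analyte and leave the other alone. Entering both results in the unit of the kit limits gives the intended ratio. Even a literal application leaves the tests unchanged, and the levels could be recovered exactly from the laboratory spreadsheets and printouts that section 10.1 treats as source documentation. Secondary analyses are also run without control of the type I error rate (section 11.2), so no confirmatory claim rests on the ratio. All of this stands, and it is why the point is minor. It does not make the printed rule correct: this is the only derivation of a named biomarker, and it gives a wrong number when followed as written.

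It may also be said that the unit is an artefact of reading the PDF, with a lost micro sign. Micro signs survive elsewhere in the text (the adipokine table in section 2.4.4.3 and the aliquot volumes in Appendix 1), so this is not the likeliest explanation, though it cannot be excluded. The units would still not match, and the factor would be 10^3.

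A reader might go further and infer two things that the documents do not support.

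- *That change from baseline in the ratio becomes uninterpretable.* It does not. A uniform factor rescales the change by a known power of ten and leaves its sign and every test as they were.
- *That mixed units across batches would corrupt the pre/post or between-arm comparison.* Nothing in the documents suggests that batches would be handled differently. Item 4 has each subject's pre- and post-study samples run together, so a batch-level slip would not normally split a pair. Enrolling and coordinating site staff are blinded (section 4.6.2), so a slip should not follow treatment arm. Section 10.1 already provides accuracy checks and statistician review of summary reports. It does not name units, but a million-fold discrepancy is easy to see.

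**Conclusion.** The unit mismatch is real, and it stands in operative text. Applied literally, the formula gives values 10^6 too small for every reported ratio, change and confidence limit, or 10^3 too small if micrograms were meant. The factor is exact and does not depend on any assumed concentration. It arises only if IGF-I is actually converted to the printed unit; kit output entered in ng/ml for both analytes gives the correct ratio.

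Given uniform application, between-arm p-values and correlations are unaffected. The primary endpoint and sample size are not touched. This is a minor correction to the derivation of one secondary biomarker. It is not a threat to the trial's inference.

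**What to change.** In Appendix 1, item 4, state the formula as [.130 x IGF-I (ng/ml)]/[.036 x IGFBP-3 (ng/ml)], which agrees with the unit of both kit descriptions in that item. The cost is a one-word correction. It needs no new data and no change to design, visits, assays or planned tests. No further data check is needed for this point, because the accuracy checks in section 10.1 already cover laboratory data.

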5.1 Breast Tissue Cytomorphology

Two slides are made from each pooled sample by a liquid-based technique (ThinPrep®): two for cytomorphology under RNAse-free conditions one of which will undergo microdissection, processing to RNA and then cDNA and frozen at -80°C until later use for RT-qPCR. Remaining cells will be left in PreservCyt® for later use for RT-qPCR. Initial cytomorphologic assessment is performed by the cytotech and then the slide is photographed and sent to the cytopathologist, [name] for final assessment. Slides will be given both a categorical classifier (non-proliferative or normal, hyperplasia, hyperplasia borderline atypia, atypical hyperplasia, or suspicious for cancer) and a Masood Index score [106]. The Masood score is the result of 1-4 points given for 6 different morphologic characteristics: cellular arrangement (monolayer, overlapping nuclei, clustering, loss of cohesion), pleomorphism, myoepithelial cells (many, moderate, few, absent); anisonucleosis (absent, mild, moderate, conspicuous); nucleoli (absent, micronucleoli, micro and rare macronucleoli, predominately macronuclei); and chromatin clumping (absent, rare, occasional, frequent). Change in Masood score will be assessed by subtracting the off-study score from the baseline score

5.2 Processing of Fixed Breast Tissue for RT-qPCR

Good quality RNA is obtained from Cytolyt® fixed cells when they are processed and Pap-stained under RNAse-free conditions if >500 epithelial cells are used and RNA is harvested within 72 hours of Pap-staining, or after a year or more if they are stored in the refrigerator unstained in PreservCyt® fixative [Petroff, 2006]. Following RNA isolation, the RNA undergoes one round of linear amplification, is converted to cDNA and stored at -80°C until assayed by RT-qPCR [122]. Currently 83% of LCM epithelial samples yield good quality RNA/cDNA using the above methods and we can reliably measure gene expression by RT-qPCR for a minimum of 25 genes from approximately one-quarter to one-third of the formalin-fixed aspirate. Specimens from PreservCyt® vials are first processed and Pap-stained under RNAse-free conditions and then checked by light microscopy to assure that similar types of cells are present on the slides for LCM as for cytomorphology and Ki-67. At least 500-1000 cells from the epithelial clusters on the ThinPrep® Slides are harvested by LCM within 72 hours of Pap-staining using an AutoPix™ Automated Laser Capture Microdissection System (MDS Analytical Technologies; Sunnyvale, CA). RNA is isolated using column based chromatography and treated with DNase to eliminate any residual DNA (RecoverAll™ Total Nucleic Acid Isolation kit, Ambion/Applied Biosystems). RNA is then linearly amplified using MessageAmp™ II RNA Amplification kit (Ambion/Applied Biosystems). The amplified aRNA is reverse-transcribed to cDNA using SMARTScribe Reverse Transcriptase (Clontech Laboratories, Inc., Mountain View, CA) primed with random nonamers. Quality of RNA/cDNA is determined by the QC Metric Assay [Petroff, 2006]. Primer/probe sets are designed, using Primer Express™ v 2.0, as close as possible (ideally within 300 bp) to the 3' end of each transcript, because the amplified RNA is 3'-biased.

5.3 Ki-67 Immunocytochemistry

For Ki-67 assessments, an extra slide will be made from PreservCyt® material and total epithelial cells will be delineated with Mayer's hematoxylin counterstain and proliferating cells with a MIB-1 (DAKO M7240) antibody and citrate buffer antigen retrieval. A DAKO automatic stainer is used for all stains to insure staining consistency. Manual counting is performed by two laboratory technicians. Hyperplastic ducts (if present) with the highest concentration of MIB-1 positively staining cells are selected for analysis and a minimum of 500 total ductal cells are scored. The consensus score is utilized for analysis.

5.4 Processing of Frozen Breast tissue for RT-qPCR

RNA isolation can be performed on fresh frozen tissue which has not undergone LCM. This is most useful for high abundance genes expressed in stroma and fat +/- epithelium such as adiponectin and leptin. A 250 µl aliquot of pooled thawed RPFNA specimen is removed and mixed with 750 µl TRIzol® LS (Invitrogen Corporation, Carlsbad, CA) at room temperature. After at least 5 minute incubation at room temperature the TRIzol® LS-sample mixture can be stored at -80°C for later RNA extraction. RNA is extracted from the TRIzol® LS-sample mixture according to the manufacturer's protocol, including glycogen (Invitrogen) as a carrier prior to RNA precipitation. RNA amplification, reverse transcription, and PCR analysis are performed in the same way as for formalin-fixed RPFNA samples [122].

5.5 Frozen Tissue Adipokine and Cytokine, Analysis

250 μ l aliquots of frozen RPFNA will be labeled with date, HRBC #, and Study # and stored at -80°C until shipment to [name] at the University of Texas at Austin for analysis via kits supplied by Luminex [120,121].

5.6 Frozen Tissue Reverse Phase Proteomics:

250 μ l aliquots of frozen RPFNA will be labeled with date HRBC # and Study # and stored at -80°C until shipment to [name] at MD Anderson Cancer Center for immunoblotting with specific antibodies and analysis via ImageQuant with Viagene Software [123-125].

6. Assessment of Single Nucleotide Polymorphisms

Samples of buccal cells collected in Scope® mouthwash will be used to assay for single nucleotide polymorphisms,(SNPs) thought to be associated with influencing risk for developing breast cancer by virtue of modulating a variety of cellular and metabolic processes. Specifically, variants of CYP17 will be assayed since it has been hypothesized to affect lignin levels. Samples are stable in the mouthwash for months at room temperature and no special handling. Specimens will be shipped to [name] at Intergenetics, in Oklahoma City, OK, for assessment [114,115], at an alternate laboratory if necessary, or will be assayed at KUMC.

7. Lignans

7.1 Measurement of Plasma Lignans

Fasting plasma will be shipped to Cincinnati Children's Hospital where it will be assessed by HPLC analysis with Waters Quattro Micro UPLC system coupled to electrospray tandem mass spectrometry (ESI-MS/MS) by [name] [111].

7.2 Measurement of Urine Lignans

Spot and overnight (12 hour) collections of urine will be shipped to Fred Hutchinson Cancer Research Center for measurement by [name] using isotope dilution gas chromatography-mass spectrometry in SIM mode [41,112,113], with normalization by creatinine level.

8. Questionnaires

8.1 The BCPT symptom checklist is a 42 item list of problems common to peri and postmenopausal women and those undergoing anti-hormonal treatment in prevention trials. Women are asked if they have had the symptom in the past four weeks. If they answer yes, they are asked to grade the severity (0-4). This tool can be used to compute a total score or individual or related items of interest (e.g., three items relate to joint stiffness and arthralgias) may be scored [117,118].

8.2 The Breast Pain Questionnaire (BPQ), a modified short form of the McGill Pain questionnaire (SF-MPQ), will be used to assess breast discomfort and a possible effect of SDG to ameliorate symptoms of mastalgia [116].

8.3 Changes in menstrual cycle length will be assessed by having subjects complete a menstrual diary for each month they are on study.

8.4 Lignan intake will be assessed at study entry using a questionnaire modified after that developed by Thompson et al. [16,42] which queries intakes and amounts of ~125 foods containing significant amounts of SECO, pinoresinol, matairesinol, and sesamin, all of which can be converted to the mammalian lignans ENL and EDL [16].
